### 18.4.2. Anticipated serious adverse device effect (ASADE)

Anticipated serious adverse device effect is any event that by its nature, incidence, severity, or outcome has been previously identified in the risk analysis report. In this investigation no SADE are anticipated.

### 18.4.3. Unanticipated serious adverse device effect (USADE)

An unanticipated serious adverse device effect is a serious adverse device effect which by its nature, incidence, severity or outcome has not been identified in the current version of the risk analysis report.

### 18.5. Medical care of subjects

Principal investigator shall ensure that adequate medical care is provided, during and after participation in the clinical investigation, to a subject experiencing an adverse event. All ongoing ADEs, SAEs, SADEs and DDs that could have led to a SAE at subject termination will be followed according to the Risk Benefit analysis (see 8.2) and will be followed until a resolution is addressed for a period of 2 months after subject termination. An ongoing adverse event at subject termination visit is documented as the current status for the adverse event and will not be followed up.

The subjects shall be informed of any new significant findings occurring during the clinical investigation, including the need for additional medical care that can be required, and of the nature and possible cause of any adverse events experienced.

Principal investigator shall provide the subject with the necessary instructions on proper use, handling, storage and return of the investigational device when it is used or operated by the subject.

### 18.6. Reporting and timelines

### 18.7. Investigator's reporting responsibilities

PI at each site must assess all (S)AE's that occur at his/her site.

- All serious adverse events and serious adverse device effects must be reported to sponsor within 24
  hours of the site becoming aware of the event.
- A device deficiency that could have led to a serious adverse event but did not because suitable action was taken, intervention had been made or because of fortunate circumstances should be reported to sponsor within 24 hours of the site becoming aware of the event.
- New findings and/or updates in relation to already reported serious events should also be reported to sponsor within 24 hours of the site becoming aware of the event.
- Device deficiencies and all adverse device effects related to CE marked Coloplast investigational product and/or comparator must be reported to sponsor within 24 hours of becoming aware of the event.

When reporting the SAE, the relationship to the test material shall be described whether the event is considered

- Not related, the event has no temporal relationship with the use of the test material or the procedures.
- Unlikely related, the relationship with the use of the test material seems not relevant and/or the
  event can be reasonably explained by another cause, but additional information may be obtained.
- Possible related, the relationship with the use of the test material is weak but cannot be ruled out completely. Alternative causes are also possible (e.g. an underlying or concurrent illness/ clinical condition or/and an effect of another device, drug or treatment). Cases where relatedness cannot be assessed or no information has been obtained should also be classified as possible.
- o **Probable related,** the relationship with the use of the test material seems relevant and/or the event cannot reasonably be explained by another cause, but additional information may be obtained.
- Definitely related/Causal relationship, the event has a temporal relationship with the test material use/application or procedures.

and the intensity of the event should be considered, as such:

- o **Mild**, the intensity of the event is mild with no further action or intervention.
- o Moderate, the intensity of the event will lead to an action or intervention to solve the event
- Severe, the intensity of the event will lead to follow up on the action or intervention, as the effect of the action or intervention may not decrease the symptoms.

All above events must be reported by use of the relevant adverse event/serious adverse event/device deficiency form. The Senior Clinical Manager is responsible of informing the Chief Investigation about all SAE's.

Please report to:

Coloplast A/S [name]

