### 18.2. Adverse device effect

An adverse event, which is related to the use of the investigational medical device, is an adverse device effect, and should be marked as unlikely related, possible related, probable related or with causal relationship on the adverse event form.

The definition of an adverse device effect includes any event resulting from insufficiencies or inadequacies in the instruction for use, deployment, implantation, installation and operation, or any malfunction of the medical device, as well as any event resulting from use error or from intentional misuse of the device.

Table 2 lists anticipated adverse device effects that may occur.

Table 3 Anticipated adverse device effects and their likely incidence rates.

| ANTICIPATED ADE                                      | INCIDENCE RATE |
|--|----------------|
| Peristomal skin irritation (incl. mechanical trauma) | < 10%          |
| Allergic peristomal skin irritation (dermatitis)     | < 1%           |

Temporary redness upon removal of the base plate is not considered an adverse device effect, however an abnormal development in intensity or duration should be considered as such.

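### Section 18.7 defines Definitely related by timing alone, so one serious adverse event can meet both Unlikely and Definitely; separately, 18.2 leaves unclear whether Unlikely events count as device effects

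*Combined protocol and SAP*

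**What the plan says.** Section 18.7 introduces the ratings with "When reporting the SAE, the relationship to the test material shall be described whether the event is considered" and then lists five:

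- *Not related*: "Not related, the event has no temporal relationship with the use of the test material or the procedures".
- *Unlikely*: the relationship seems not relevant, and/or the "event can be reasonably explained by another cause, but additional information may be obtained".
- *Possible*: "the relationship with the use of the test material is weak but cannot be ruled out completely". Other causes are allowed, and events that cannot be assessed go here.
- *Probable*: "the relationship with the use of the test material seems relevant and/or the event cannot reasonably be explained by another cause".
- *Definitely*: "Definitely related/Causal relationship, the event has a temporal relationship with the test material use/application or procedures".

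Section 18.2 says that an event "which is related to the use of the investigational medical device, is an adverse device effect, and should be marked as unlikely related", and its list goes on through possible and probable to causal. It gives no criterion for any of these labels.

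Section 18.4.1 defines a serious adverse device effect (SADE) as an ADE with a serious outcome, and 18.4.2 anticipates none. On reporting, 18.7 says "All serious adverse events and serious adverse device effects must be reported to sponsor within 24" hours. Section 18.8 has the sponsor report every SAE to the authorities within 7 calendar days. Section 10.1 assesses adverse events on the safety population and does not mention relatedness.

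**The concern.** A causality scale should run from no link to a certain link, with each step asking for more evidence. Here the top step asks for less than the one below it. *Probable* at least requires that the relationship seem relevant or that no other cause explain the event. *Definitely* requires only timing. The two ends of the scale are therefore opposites on timing, and *Definitely* overlaps all three ratings between them.

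The study has no comparator (4.9), so attribution of events to the device rests on these ratings. SAEs with another possible cause are foreseeable. Appendix 9 sends hospital admissions to the AE/SAE form and gives dehydration, skin issues and stoma issues as unplanned reasons. Section 18.4 removes only planned hospitalisation for a pre-existing condition, or a procedure the plan requires, without serious deterioration. At stake is whether the reported ratings, and the ADE and SADE counts, mean what a reader will take them to mean.

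**Working it through.** No figure in the plan is involved, so the check sets the definitions side by side.

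**Exposure.** Section 5.1 gives 12 weeks ±2 weeks, which is 12 × 7 = 84 days (10 × 7 = 70 to 14 × 7 = 98). Section 4.8 supplies sensor layers for daily change. If onset during wear counts as a temporal relationship, nearly every event after V1 has one. The plan does not define the term; this is its natural reading.

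**Two test events, read literally.** Event A is an SAE during wear that another cause reasonably explains. Event B is the same, except that the relationship to the device also seems relevant.

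| Rating in 18.7 | Event A | Event B |
|---|---|---|
| Not related | barred by timing | barred by timing |
| Unlikely | met: another cause is enough on its own | met: same limb |
| Possible | met only if the link is judged weak but not ruled out | as A |
| Probable | second limb fails; met only if the link seems relevant | met: first limb is enough on its own |
| Definitely | met: timing is the only test | met: timing is the only test |

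Event A meets *Unlikely* and *Definitely*. Event B meets *Unlikely*, *Probable* and *Definitely*. The and/or produces the overlap between *Unlikely* and *Probable*, because either limb of each definition is enough. No other section adds a criterion or says which rating to choose when two apply.

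**Section 18.2.** By its defining phrase, an ADE is related to device use, which suggests that an *Unlikely* event is not one. By its rating list, an *Unlikely* event is one. Section 18.4.1 builds SADE on ADE, so the ambiguity carries over to serious events.

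**What depends on the rating.** For SAEs, the 24-hour report (18.7), the 7-day report (18.8) and follow-up of ongoing events (18.5) apply whatever the rating. For non-serious events, ADE status does matter: 18.7 requires ADEs to be reported within 24 hours, and 18.5 follows ongoing ADEs for 2 months after termination but does not follow other ongoing non-serious events.

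**The case against.** The strongest reply is that sites will not apply the text literally. The rating is also labelled a causal relationship and stands at the top of a graded list. Investigators must assess each event, and site staff are trained in adverse event reporting (8.4). Few assessors would call causal an event that they believe another cause explains. This limits the size of the problem: where sites rate by judgement, nothing is misrated. It does not remove it, because timing is the only criterion given, and up to 10 sites may split between text and judgement.

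A second reply is that one scale may already be meant for all events. Section 18.7 opens with the assessment of serious and non-serious events, and 18.2 puts nearly the same labels on the adverse event form. That is a fair reading, but the definitions are introduced for the SAE, so the plan should say which applies. The form itself is not in the documents.

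A reader might infer that choosing *Definitely* over *Unlikely* turns an admission with another cause into an unanticipated SADE, since 18.4.2 anticipates none. The documents do not support this. The list in 18.2 holds both ratings, so on that list the event is an ADE, and if serious a SADE, either way. The choice changes the label and not the count. The count turns on how the contradiction within 18.2 is settled.

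**Conclusion.** The definitions are wrong as written, and the correction is minor. *Definitely* is a timing test, an SAE during wear with another reasonable cause literally fits two opposed ratings, and the and/or adds a second overlap. The contradiction in 18.2 is a separate fault, and it is the one that governs the ADE and SADE counts.

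The size can only be bounded. At one end, if all sites rate by judgement, no event is misrated. At the other, if all follow the text, every SAE during wear that another cause explains could be rated *Definitely*. The documents give neither an SAE rate nor a misrating rate. Assuming an SAE rate would show only how likely such an event is to occur, and not how likely it is to be misrated, so no probability is given.

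No SAE report or SAE follow-up is lost, and the primary and secondary efficacy analyses are unaffected. The conclusion assumes that onset during wear counts as a temporal relationship.

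**What to change.** 1. In 18.7, add to *Definitely*, beside timing, that no other cause reasonably explains the event.
2. Reword *Unlikely* and *Probable* without and/or. Step 1 alone is not enough: the second limb of *Probable* is already the lack of another reasonable cause, so the two top grades would then coincide. One form that works, for events with a temporal relationship, is *Unlikely* when another cause is the more reasonable explanation and *Probable* when another cause is less likely but not excluded. *Possible* can keep its text if a sentence reserves it for such events that fit none of the other grades. Event A then falls under *Unlikely*, and Event B goes wherever the comparison of causes puts it, once only.
3. Reconcile the defining phrase in 18.2 with its own rating list and with 18.4.1, so that it is clear whether *Unlikely* events are ADEs and, if serious, SADEs.
4. In 10.1, report adverse events and SAEs by relatedness grade, so that counts with and without *Unlikely* can both be read off.
5. The sponsor should state whether the scale covers non-serious events, and how any change affects ADE reporting (18.7) and follow-up (18.5).

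The cost is wording in 18.7 and 18.2, a matching form and training note for the sites, and a tabulation by grade. SAE reporting does not change. Step 5 needs care. If the scale covers non-serious events and *Not related* keeps its timing-only test, a headache during wear (an example in 18.1) could not be *Not related*. On the 18.2 list it would then count as an ADE, with 24-hour reporting. Whether that is intended is for the sponsor to say.

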### 18.8. Sponsors reporting responsibilities

It is the responsibility of sponsor to ensure that the following are reported to national regulatory authorities immediately, but no later than 7 calendar days following the date of awareness by sponsor.

- All serious adverse events.
- All serious device effects.
- All device deficiencies that could have led to serious adverse events but did not because suitable action was taken, intervention had been made or because of fortunate circumstances.
- New findings and/or updates in relation to already reported events.

If the serious adverse event results in imminent risk of death, serious injury, or serious illness that requires prompt remedial action for other subjects, users or other persons or a new finding to such a serious adverse event, sponsor must immediately but no later than 2 calendar days after awareness by sponsor report the event to national regulatory authorities.

It is the responsibility of sponsor to inform all investigators in writing within 10 working days if device deficiencies, adverse events, adverse device effects, near-incidents, serious adverse events, serious adverse device effects or unanticipated serious adverse device effects lead to corrective actions (e.g. change of IFU).

### 18.9. Data Safety and Monitoring Board (DSMB)

The review of all safety data will be conducted on an ongoing basis to identify any potential safety issues. If needed, the coordinating investigator can call for a Data Safety and Monitoring Board meeting with relevant members, to discuss potential safety issues and further recommendations, if relevant.

Based on the safety data review, the coordinating investigator along with the DSMB may recommend that the sponsor modifies, temporarily suspends, or terminates the clinical investigation.

Correspondence, decisions, and recommendations regarding safety in the Clinical Investigation from the Data Safety and Monitoring Board must be documented in meeting minutes and saved electronically in the Sponsor File.

All final decisions, however, regarding clinical investigation modifications, remain with the Sponsor.

### 19. Suspension or premature termination of the clinical investigation

Sponsor may suspend or prematurely terminate an investigation site or the entire clinical investigation for documented significant reasons.

If a suspicion of an unacceptable risk to subjects develops during the clinical investigation, sponsor will suspend the investigation while the risk is assessed. Sponsor will terminate the investigation if an unacceptable risk is confirmed. Sponsor will ensure that the premature termination will be justified in writing and will promptly inform the regulatory authorities and relevant EC(s). If monitoring or auditing of the clinical investigation identifies serious or repeated deviations at one of the participating investigation sites, sponsor will suspend or terminate the particular investigational site. The sponsor or investigator will inform the regulatory authority as appropriate and notify the EC about the termination of the site.

If suspension or termination of the clinical investigation occurs, the investigator(s) will promptly inform the enrolled subjects. Sponsor will provide resources to fulfil the obligations from the CIP for follow-up on the subjects as necessary.

### 20. Clinical investigation report

At completion of the investigation sponsor is responsible for writing the clinical investigation report. The report is retained on file. The report contains a critical evaluation of all data, which have been collected during the investigation. The report describes the methodology and design and a data analysis, including statistical preparation and conclusion.

Sponsor and coordinating investigator must sign the final version of the clinical investigation report or an affidavit, indicating their agreement with the contents. If no coordinating investigator is appointed, then the signatures of the principal investigator(s) should be obtained.

The clinical investigation report must be submitted to EC.

### 21. Publication policy

Publication policy is specified in Sponsor Investigator Agreement.

### 21.1. General

The investigation will be registered on a public accessible database, e.g. www.ClinicalTrial.gov, before recruitment of the first subject. The results of the investigation, positive as well as negative, may be communicated by abstracts, posters or oral presentations provided that opportunity is given for sponsor to discuss the contents and any conclusions drawn, before the abstract, paper or visual presentations are finalised. In all cases the subject's identity will remain confidential.

Sponsor will undertake to comment on the draft documents within 30 working days of receipt, but the final decision on the contents and format of the publication from the conclusions drawn, will remain with the authors.

No preliminary results will be published.

Data from the investigation is considered confidential until it is published according to the conditions of this CIP.

Sponsor may publish single subject case stories at any time during and after the investigation.

Sponsor reserves the right to use the data (published and unpublished) for reimbursement or regulatory purposes.

### 21.2. Joint publication

A joint paper will not be published before all PIs have approved the content of the clinical investigation report. If a site cannot approve the results/conclusions drawn, an independent EC will be asked to review, and all investigators must follow its conclusion.

Decisions regarding authorship credit will follow the "Uniform Requirements for Manuscripts submitted to Biomedical Journals" (the Vancouver group) according to which an author of a publication must fulfil the following criteria:

- Substantial contribution to conception and design, or acquisition of data, or analysis and interpretation
  of data.
- Drafting the article or revising it critically for important intellectual content.
- Final approval of the version to be published.

Investigators who do not meet all the above criteria for authorship will be listed in the acknowledgment section under the heading "clinical investigators" and their function or contribution described. All persons must give written permission to be acknowledged.

### 21.3. Individual publication

Individual sites may only publish their own data from the investigation (case histories not included) in the case that:

- No joint publication is planned, or a joint paper has already been published.
- Approval from sponsor has been obtained.

### 24. Appendix

## 24.1. Appendix 1 - Bristol scale

# The Bristol stool form scale

The stool type illustrations below will help you determine your stool type.

| Type 1   | Type 2  | Type 3  | Type 4  | Type 5   | Type 6  | Type 7   |
|--|---|---|---|--|---|--|
|  |   |   |   | 30   |   | 4  |
| Separate
hard lumps,
like nuts
(hard to pass)                         | Sausage-
shaped but
lumpy   | Like a sausage
but with cracks
on its surface | Like a sausage
or snake,
smooth and
soft | Soft blobs
with clear-cut
edges (passed
easily) | Fluffy pieces
with ragged
edges, a
mushy stool | Watery, no
solid pieces,
entirely liquid |
| Lews SJ, Heaton KW (1997), "Stool fo
Scand. J. Gastroenterol., 32 (9):920-4 | .ews Sj. Heaton KW (1997). "Stool form scale as a useful guide to Intestinal transit tume"
icand   Gastroenterol, 32 (9):920–4 | to intestinal transic time.                         |   |  |   |  |

24.2. Appendix 2 - Leakage scale questionnaire (OLI)

Emotional impact

When you thought about your ostomy device and the risk of leakage, what emotions did you feel?

| In the last 7 days, due to leakage or worry about leakage | All of the time | Often | Sometimes | Rarely or never |
|---|-----------------|-------|-----------|-----------------|
| 1. I felt panic   | 0               | 1     | 2         | 8               |
| 2. I felt stressed out                                    | 0               | 1     | 2         | 3               |
| 3. I felt more afraid about leaks in the future           | 0               | 1     | 2         | က               |
| 4. I felt worry   | 0               | 1     | 2         | ю               |
| 5. I felt frustrated                                      | 0               | 1     | 2         | 9               |
| 6. I felt embarrassed                                     | 0               | 1     | 2         | е               |
| 7. I felt worried that I might leak                       | 0               | 1     | 2         | r               |
| 8. I couldn't sleep                                       | 0               | ٠     | 2         | 3               |
| 9. I kept waking up at night to check my stoma            | 0               | 1     | 2         | е               |
| 10. I kept checking my ostomy bag to see if I have leaked | 0               | -     | 2         | m               |

Usual and Social activities

When you thought about your ostomy device and the risk of leakage, how did it affect your activities?

|  | All of the time Often | Often        | Sometimes | Rarely or
never | Not appli-
cable |
|--|-----------------------|--------------|-----------|--------------------|---------------------|
| In the last I days due to leakage of worry about leakage     |                       |              |           |                    |                     |
| 11. I decided to stay at home                                | 0                     | ~            | 2         | 3                  | 6                   |
| 12. I couldn't do light activities                           | 0                     | _            | 2         | 3                  | 6                   |
| 13. I changed my plans                                       | 0                     |              | 2         | 3                  | 6                   |
| 14. I was unable to go out and meet family and friends       | 0                     | -            | 2         | 3                  | 6                   |
| 15. I avoided close physical contact with family and friends | 0                     | _            | 2         | 3                  | 6                   |
| 16. I did not want to see people                             | 0                     | _            | 2         | 3                  | 6                   |
| 17. I avoided people   | 0                     | _            | 2         | င                  | 6                   |
| 18. I tried to avoid meeting new people                      | 0                     | <del>-</del> | 2         | ဇာ                 | o            |
|  |                       |              |           |                    |                     |

Coping and in control

When you thought about your ostomy device and the risk of leakage, how did it affect your ability to cope?

| In the last 7 days, due to leakage or worry about leakage | All of the time | Often    | Sometimes | Rarely or never |
|---|-----------------|----------|-----------|-----------------|
| 19. I felt in control                                     | 0               | ~ | 2         | ဧ               |
| 20. I was able to cope                                    | 0               | _        | 2         | 3               |
| 21. I felt calm   | 0               | -        | 2         | 3               |
| 22. I saw my friends as I usually do                      | 0               | -        | 2         | 3               |

